**NON-INTERVENTIONAL (NI) STUDY PROTOCOL****Study information**

Title	Treatment patterns of menopausal hormone therapy in South Korea: a nationwide cohort study
Protocol number	B2311076
Protocol version identifier	2.0
Date	June 27, 2023
Active substance	Conjugated estrogens and bazedoxifene (G03CC07)
Medicinal product	Duavive® tablet 0.45mg/20mg
Research question and objectives	
Research question: What are the real-world usage patterns of menopausal hormone therapy in South Korea?
 
Objectives
 
1. To estimate the prevalence of menopausal hormone therapy by treatment class, age group, menopausal symptoms, and the type of administration2. To describe the baseline characteristics of patients prescribed with or without menopausal hormone therapy3. To examine treatment patterns, adherence, and persistence among patients with menopausal hormone therapy
Author	PPD , RPh, MPH. PPD , Pfizer Korea e-mail: PPD PPD , PhD. PPD School of Pharmacy, Sungkyunkwan University (SKKU) e-mail: PPD

This document contains confidential information belonging to Pfizer. Except as otherwise agreed to in writing, by accepting or reviewing this document, you agree to hold this information in confidence and not copy or disclose it to others (except where required by applicable law) or use it for unauthorized purposes. In the event of any actual or suspected breach of this obligation, Pfizer must be promptly notified.

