9.3. Variables

9.3.1 Exposure

As our main goal of this study is to understand current treatment patterns of MHT, exposure will be defined as the medications prescribed most likely to treat menopausal symptoms based on current treatment guideline. We will classify treatment classes of MHT as below:

Table 2. Prescription drugs for inclusion

MHT type	Ingredient	Ingredient code
Estrogen therapy (ET)	Estradiol hemihydrate	154901ATB 154902CCM 154903ATB 154904CPC 154905CPC 154906CPC 154907CSI 154908CCM 154908COM

PFIZER CONFIDENTIAL

		154930CCM 154931CCM 154932CCM
	Estradiol valerate	155001ATB 155002ATB
	Conjugated estrogens	155301ATB 155303CCM 155401ATB 155402ATB 155402CCM 155404ATB 155430CCM
	Estriol	155201CCM 155202CSP
	Estriol/Lactobacillus Acidophilus	507700CTB
	Ethynodiol diacetate	156401ATB
	Estradiol	154601CPC 154602CPC 154603CPC 154604CPC 154605CPC 154606CPC
	Estradiol/Lactobacillus Acidophilus	336200CTB
	Estropipate	155501ATB 155502ATB 155502CCM
	Promestriene	219001CCS 219001CCM 219030CCM 336100CTB
Estrogen + Progestin Therapy (EPT)*	Estradiol hemihydrate/Norethisterone acetate	297000ATB 297100ATB 298200ATB
	Estrodiol or Estradiol hemihydrate/Dydrogesterone	297400ATB 433700ATB 433800ATB
	Estrodiol hemihydrate/Drospirenone	490400ATB
	Estradiol valerate/Norethisterone acetate	507600ATB

	Estradiol valerate/Medroxyprogesterone acetate	297600ATB 297700ATB 433900ATB 434000ATB 434100ATB 441800ATB
	Estradiol valerate/Cyproterone acetate	297800ATB 398400ATB
	Estradiol valerate/Levonorgestrel	297500ATB 298000ATB
	Estradiol valerate/Norgestrel	297900ATB
	Conjugated estrogen/Medroxyprogesterone acetate	297200ATB 297300ATB 298100ATB 424600ATB 424700ATB 424800ATB 424900ATB 453500ATB 465500ATB
	Estradiol/Norethindrone acetate	335900CPC
	Estradiol/Norethistrone acetate	336000CPC
	Dydrogesterone†	150501ATB
	Medroxyprogesterone acetate†	188901ATB 188903ATB 188904ATB 188905ATB 188906ATB
	Micronized progesterone †	195001ACS
	Cyproterone acetate†	139401ATB
	Norethisterone†	203201ATB
Tibolone	Tibolone	239001ATB

*Estrogen and progestin in combination and estrogen monotherapy plus progestin monotherapy will be included.

†Regarding Estrogen monotherapy plus Progestin monotherapy, only both estrogen and progestin within the same prescription will be considered as progestin therapy as progestin therapy is only approved for use in combination with estrogen.

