 - First, we will examine trends by 3 classes of MHT: ET (estrogen therapy), EPT (estrogen-progestin therapy) and tibolone. The time-series trend will be presented as the proportion of each class of MHT quarterly, calculated as the number of patients receiving each class of MHT divided by the total number of patients prescribed with MHT.
 - Second, we will examine trends by age group: all, 40-44, 45-49, 50-54, and 55-59. The time-series trend will be presented as the proportion of MHT use by each age group, calculated as the number of patients in each age group divided by the total number of patients prescribed with MHT.
 - Third, we will examine trends by menopausal symptoms: vasomotor symptoms, bone and joint symptoms, genitourinary symptoms, and psychosomatic symptoms. The time-series trend will be presented as the proportion of MHT use by each menopausal symptom, calculated as the

number of patients with each menopausal symptom divided by the total number of patients prescribed with MHT.

- Fourth, we will examine trends by the type of administration: systemic HT (oral), systemic HT (transdermal) and local HT (transvaginal). The type of administration of MHT will be classified as follows (Table 4). The time-series trend will be presented as the proportion of MHT use by each type of administration, calculated as the number of patients with MHT by each type of administration divided by the total number of patients prescribed with MHT.

Table 4. Type of administrations

Type of administrations	Ingredient code
Systemic HT (oral)	All ingredient codes except those for systemic HT (transdermal) and local HT (transvaginal)
Systemic HT (transdermal)	154902CCM 154904CPC 154905CPC 154906CPC 154907CSI 154908CCM 154908COM 154930CCM 154931CCM 154932CCM 154601CPC 154602CPC 154603CPC 154604CPC 154605CPC 154606CPC 335900CPC 336000CPC

Local HT (transvaginal)	155303CCM 155402CCM 155430CCM 155201CCM 155202CSP 507700CTB 336200CTB 155502CCM 219001CCS 219001CCM 219030CCM 336100CTB
-------------------------	--

4) Treatment regimens change of MHT across time

- We will depict treatment switch and discontinuation patterns across time by measuring the number of different treatments, including ET, EPT and tibolone, at time points of 3, 6, 9, and 12 months from the index date. Switching and discontinuation of MHT across time will be presented with a Sankey diagram.

5) Time to switch and discontinuation of MHT

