9.3.3 Baseline characteristics

We will identify the demographic and clinical characteristics of patients with menopausal hormone therapies.

- On cohort entry date
 - Age (40-44, 45-49, 50-54, 55-59)
 - Insurance type (national health insurance, medical aid)
 - Medical institution type (tertiary hospital, hospital, clinic)
- During 1-year prior to cohort entry date
 - CCI (Charlson Comorbidity Index)
 - No. of outpatient visits
 - No. of hospitalization
 - Comorbidities (diabetes mellitus, hypertension, dyslipidemia, cancer, anemia)

Table 5. Comorbidities

Comorbidities	KCD-8 code
Diabetes mellitus	E10-E14
Hypertension	I10-I15
Dyslipidemia	E78
Cancer	C00-C97 (except C22, C23, C24, C50, C54.1, C56)
Anemia	D50-D53, D55-D64

- Concomitant medications (bisphosphonate, denosumab, teriparatide, SERM, vitamin D, calcium)

Table 6. Concomitant medications

Ingredient	Ingredient code

Ibandronic acid*	480301BIJ 480302BIJ 480303BIJ 480304ATB 480330BIJ 487901ATB 523900ATB
Zoledronic acid*	420701BIJ 420702BIJ 420730BIJ 420731BIJ 420732BIJ
Risedronic acid*	442301ATB 442302ATB 500901ATB 442303ATB 511200ATB 518400ATB 442302ATE 442330ATB
Pamidronic acid*	207901ACS 207902BIJ 207903BIJ 207930BIJ
Alendronic acid*	228302ATB 228301ATB 228303ATB 468000ATE 481100ATR 500200ATB 481100ATB 228303ALQ 228305ATB 228306ALQ 228307ALQ
Etidronic acid*	147401ATB
Clodronic acid*	136101ACH 136102BIJ
Denosumab	629001BIJ

	629002BIJ
Teriparatide	487502BIJ 646301BIJ
Bazedoxifene [§]	617101ATB 674500ATB
Raloxifene [§]	358001ATB 358002ATB 659200ACH 659200ATB 698200ATB
Vitamin D	121401ACS 121402ACS 121601ACS 121602BIJ 121603BIJ 121604ACS 121604ATB 121630BIJ 316800BIJ 316900BIJ 317000BIJ 387900ACS 468000ATE 481100ATB 481100ATR 500200ATB 511200ATB 518400ATB 523900ATB 659200ACH 659200ATB 674500ATB 698200ATB
Calcium	357900ATB

*Following medications will be categorized as bisphosphonate: Ibandronic acid, Zoledronic acid, Risedronic acid, Pamidronic acid, Alendronic acid, Etidronic acid, Clodronic acid

[§]Following medications will be categorized as SERM: Bazedoxifene, Raloxifene

- On index date

- Type of administration (systemic HT (oral), systemic HT (transdermal), local HT (transvaginal)) (Table 4)

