9.9. Strengths and limitations of the research methods

Due largely to its nature of medical claims data, there are some inbuilt limitations. Firstly, discrepancies occur between diagnoses entered in HIRA data and diseases that a patient actually has in reality. Such discrepancies may arise from the inherent nature of claims data, in which the diagnostic codes used for reimbursement might reflect suspected clinical diagnoses rather than confirmed clinical diagnoses. In addition, there is a lack of clinical laboratory data and other clinical markers. Lastly, claims data only provide information on filled prescriptions, not medications actually used. It is also applicable for non-reimbursable diagnosis, treatment or medications. These limitations are generally undetectable or unsolvable, but the dominant majority of data is valid according to the previous studies on the feasibility of the NHIS (National Health Insurance Service) and the HIRA claims data in South Korea. Despite these limitations, we will use HIRA data because it has enormous valuable information representing the entire population of South Korea. We expect to produce real-world evidence on current trends in MHT in South Korea.

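### The protocol's named active substance, conjugated estrogens/bazedoxifene, is in no MHT class or exposure code row; any use of it in 2012-2020 would be misclassified

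*Combined protocol and SAP*

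**What the plan says.** The Study information table names the active substance as "Conjugated estrogens and bazedoxifene (G03CC07" and the medicinal product as "Duavive® tablet 0.45mg/20mg".

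Section 9.3.1 sets exposure by clinical purpose: "exposure will be defined as the medications prescribed most likely to treat menopausal symptoms based on current treatment guideline". Table 2 then lists the qualifying ingredient codes under ET, EPT and tibolone. Section 9.3.2 uses the same scheme: "First, we will examine trends by 3 classes of MHT: ET (estrogen therapy), EPT (estrogen-progestin therapy) and tibolone". The Table 2 footnote limits EPT to estrogen with a progestin: "Estrogen and progestin in combination and estrogen monotherapy plus progestin monotherapy will be included".

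Bazedoxifene appears in one other place, Table 6 in section 9.3.3, with the note "Following medications will be categorized as SERM: Bazedoxifene, Raloxifene". Under section 9.2, concomitant medications are assessed in the year before cohort entry.

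On drugs outside the claims, section 9.9 has one general sentence: "It is also applicable for non-reimbursable diagnosis, treatment or medications". It does not name the product.

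**The concern.** A reader who sees the product in the title table will expect the study either to describe its use or to say that it cannot. The protocol does neither, and its definitions give users of the product a specific and wrong label.

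Three results are exposed:

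- MHT prevalence (Objective 1), whose numerator needs a prescription for a listed drug.
- Any group of women without MHT (Objective 2), which would include women treated with the named product.
- The division of treatment endings into switch and discontinuation, including the Sankey diagram (Objective 3). A move to the product is a change of therapy, but it would be drawn as stopping.

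**Working it through.** The plan states no figure on this point, so the check compares code lists and then applies the written definitions.

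**Step 1: is the product in the exposure list?** Table 2 holds 39 ET codes, 39 EPT codes and 1 tibolone code: 39 + 39 + 1 = 79, all distinct. Conjugated estrogens appear alone under ET and with medroxyprogesterone acetate under EPT. No row names bazedoxifene. The two bazedoxifene codes in Table 6 are 617101ATB and 674500ATB, and their overlap with the 79 codes is 0.

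**Step 2: could a listed code still be the combination?** In Tables 2 and 6, fixed combinations typically carry 00 in positions 5-6 of the code. No code in the conjugated estrogens row of ET has that form. In Table 6, 674500ATB is also in the vitamin D row, so it reads as bazedoxifene with vitamin D, and 617101ATB looks like a single ingredient. This is an inference from row labels and code patterns; the documents contain no code dictionary.

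**Step 3: could an existing class absorb it?** EPT requires a progestin, and the protocol itself classes bazedoxifene as a SERM. Table 6 does not help either, because its window closes at cohort entry and captures nothing after the index date.

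**Step 4: apply the rules to a user.**

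- *Product only.* She has no index date, is outside the MHT numerator in section 9.3.2, and falls in any group without MHT.
- *Moves to it from ET, EPT or tibolone.* A switch is a move to another treatment class, and only three exist, so this is not a switch. She becomes a discontinuation once two months pass without a further prescription. The main definition does not say that the further prescription must be for MHT. The four-month version in section 9.7 refers to a period without any MHT, which supports that reading and has the same gap.
- *Starts on it, later receives a listed drug.* Her index date becomes the later date, so she enters as a new initiator.

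**Step 5: size, under assumed shares.** The documents give no volume for the product.

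Let s be the share of true MHT users on the product alone. Counted prevalence = (1 - s) × true prevalence:

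| s (assumed) | counted / true |
|---|---|
| 0% | 1.00 |
| 1% | 0.99 |
| 5% | 0.95 |
| 10% | 0.90 |

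Let m be the share of initiators who move to the product with the gap elapsed by the time point. Let D and S be the true discontinued and switched shares, with S including those moves. Counted discontinuation is D + m, counted switching is S - m, and the sum is (D + m) + (S - m) = D + S. With assumed D = 40% and S = 10%:

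| m (assumed) | counted D | counted S | sum |
|---|---|---|---|
| 0% | 40% | 10% | 50% |
| 1% | 41% | 9% | 50% |
| 5% | 45% | 5% | 50% |
| 10% | 50% | 0% | 50% |

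The split shifts and the total does not. Moves made less than two months before a time point do not yet appear as discontinuation there.

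**The case against.** The strongest reply is that the title table may be administrative. No objective asks about this product, and section 9.1 sets the scope as commonly used MHT. HIRA holds claims filed for reimbursement. If the product was never reimbursed, no code could have been listed, Table 2 contains no coding error, and section 9.9 already covers non-reimbursable drugs in general terms.

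Much of this stands. The documents give no marketing date, reimbursement status, code or volume for the product. They therefore cannot show whether the gap lies in the code list or in the data source. Objective 2 is also thinly specified: section 9.2 builds the cohort from women who initiated MHT, and sections 9.3.3 and 9.7 describe baseline characteristics only for patients with MHT. The effect on a group without MHT depends on that group being formed. Declaring a scope of reimbursed ET, EPT and tibolone would remove the mismatch with the title table.

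It does not remove the point. Exposure is defined by what treats menopausal symptoms, not by what is reimbursed. The general sentence in section 9.9 neither names the product nor says that moves to it look like stopping.

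A reader might go further and infer that persistence is materially biased. The documents do not support that. Section 9.3.2 counts switch and discontinuation alike as non-persistence events and ties persistence to the drugs prescribed at the index date. A woman leaving her index class for the product is non-persistent under either label, apart from event timing.

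**Conclusion.** The point holds conditionally. The omission is plain in the documents and unexplained. Its consequence depends on whether the product was used in the study window. If it was, MHT prevalence is understated by the share of users on it alone, and the switch/discontinuation split moves by the share of initiators who go over to it. Combined non-persistence is little affected.

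The size cannot be derived from the documents; the shares above are assumptions, and their range includes zero. Two stronger readings should be resisted. One is that results are known to be biased by a material amount, for which there is no usage figure. The other is that the effect vanishes if the claims hold no record of the product. Use outside reimbursement would still leave treated women counted as untreated or discontinued, so the effect is zero only if the product was not used in the window.

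**What to change.** Check the HIRA ingredient master file for the conjugated estrogens/bazedoxifene combination.

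- *If a code with claims in 2011-2020 exists:* add it to Table 2 as a separate MHT category and carry it through the prevalence, Sankey, switch and discontinuation definitions. Table 4 needs no new row, since it assigns every code not listed as transdermal or transvaginal to oral.
- *If none exists:* state in section 9.9 that the named product is not observable in these data, that results refer to reimbursed ET, EPT and tibolone only, and that moves to the product appear as discontinuation.

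The cost is one look-up plus either a table row with consequential edits or a few sentences of limitation. The downside of the first branch is a possibly sparse category in the quarterly tables and the Sankey diagram.

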2. LIST OF ABBREVIATIONS

Abbreviation	Definition
AE	Adverse Event
CCI	Charlson Comorbidity Index
EPT	Estrogen-Progestin Therapy
ET	Estrogen Therapy
HIRA	Health Insurance and Review Assessment
HT	Hormone Therapy
ICD	International Statistical Classification of Diseases and Related Health Problems
IRB	Institutional Review Board
KCD	Korean Standard Classification of Disease
KOSIS	Korean Statistical Information Service
MHT	Menopausal Hormone Therapy
MPR	Medication Possession Ratio
NHIS	National Health Insurance Service
SERM	Selective Estrogen Receptor Modulator
SNRI	Serotonin-Norepinephrine Reuptake Inhibitor
SSRI	Selective Serotonin Reuptake Inhibitor

VTE	Venous Thromboembolism
-----	------------------------

4. ABSTRACT

- **Title**

Treatment patterns of menopausal hormone therapy in South Korea: a nationwide cohort study

- **Rationale and Background**

Women experiencing menopause may undergo various changes, such as vasomotor, bone and joint, genitourinary, and psychological symptoms due to ovarian failure and sex hormone deficiency. Treatment guidelines recommend menopausal hormone therapy (MHT) for vasomotor symptoms and prevention of osteoporosis in women under 60 years of age or within 10 years of menopause and without contraindications. However, since the Women's Health Initiative report and the Million Women Study were published, the use of MHT has declined rapidly. Also, many studies have reported a potential link between MHT and increased risk of cardiovascular disease, breast cancer, and endometrial hyperplasia. Therefore, many menopausal individuals also seek treatment alternatives to MHT, including selective serotonin reuptake inhibitors (SSRIs), serotonin-norepinephrine reuptake inhibitors (SNRIs), gabapentin, and clonidine, although some of them have limited effectiveness and are also associated with specific adverse effects. Recently, in light of the position statement on MHT, several menopause societies concur on the necessity of individualized MHT. Given that there is limited evidence on latest MHT usage pattern using the most recent data in South Korea, we aim to estimate the prevalence of MHT among menopausal women and understand treatment patterns, adherence, and persistence among patients with MHT in South Korea using the nationwide claims database from 2011 to 2020.

- **Research Question and Objectives**

- Research question: What are the real-world usage patterns of MHT in South Korea?
- Objectives
 - 1. To estimate the prevalence of MHT by treatment class, age group, menopausal symptoms and the type of administration
 - 2. To describe the baseline characteristics of patients prescribed with or without MHT
 - 3. To examine treatment patterns, adherence, and persistence among patients with MHT

- **Study design**

A retrospective observational study using the administrative healthcare claims data

- **Study Population Eligibility Criteria**

- **Inclusion criteria**

- Patients aged 40-59 years at cohort entry date.
 - Patients who had at least one inpatient or outpatient diagnosis of menopausal symptoms between January 1, 2012 and December 31, 2019.

- **Exclusion criteria**

- Patients diagnosed with breast cancer (C50, D05), endometrial cancer (C54.1) and granulosa cell tumor (C56) within 1 year prior to the index date.
 - Patients diagnosed with coronary heart disease (I20-I25, I51.6), stroke (I60-64), and VTE (I80.2, I80.3 I26) within 1 year prior to the index date.
 - Patients diagnosed with viral hepatitis (B16-B19), cirrhosis (K70.2-K70.4, K71.7, K72.0-K72.1, K72.9, K74.0-K74.6, K76.1, K76.6-K76.7, R18, I85.0, I85.9, I86.4, I86.8, I98.2-I98.3), and hepatic cancer (C22) within 1 year prior to the index date.
 - Patients diagnosed with gallbladder disease (K80, K81, K82, K83, K85.1), gallbladder cancer (C23), extrahepatic bile duct cancer (C24) within 1 year prior to the index date.

- **Variables**

- **Exposures**

- Estrogen therapy (ET)
 - Estrogen plus Progestin therapy (EPT)
 - Tibolone

- **Outcomes**

- Prevalence of menopausal symptoms and use of MHT among women aged 40-59 years
 - Prevalence of each menopausal symptom among patients with MHT
 - Secular trend in the prevalence of MHT by treatment class, age group, menopausal symptoms and the type of administration
 - Treatment regimens change of MHT across time at 3-, 6-, 9-, and 12-month

- Time to switch and discontinuation of MHT
- Adherence and persistence of MHT during the follow-up
- Baseline characteristics
 - Demographic characteristics (age, insurance type)
 - Medical institution type
 - Proxies of health status: Charlson Comorbidity Index (CCI), No. of outpatient visits, No. of hospitalization
 - Comorbidities
 - Concomitant medications
 - Type of administration
- **Data sources**
 - The Health Insurance and Review Assessment (HIRA) claims database
 - Korean Statistical Information Service (KOSIS)
- **Study size**

We estimated the expected number of eligible patients using a medical claims volume search tool operated by HIRA (available at: <http://opendata.hira.or.kr/op/opc/olap3thDsInfo.do>). We retrieved the number of patients with menopausal and other perimenopausal disorders (N95) recorded as primary diagnosis codes and the number of patients with menopausal and other perimenopausal disorders was identified as 4,293,747 from 2012 to 2019 which is likely to have sufficient power for the study.
- **Data analysis**
 - Annual time-series prevalence of menopausal symptoms and use of MHT will separately be calculated among total women aged 40-59 years.
 - Prevalence of each menopausal symptom including vasomotor symptoms, bone and joint symptoms, genitourinary symptoms, and psychosomatic symptoms will be calculated among patients with MHT.

- Within final study cohort, prevalence of menopausal hormone therapy by treatment class, age group, menopausal symptoms and the type of administration will be calculated for each year.
- Baseline characteristics including demographic characteristics, medical institution type, proxies of health status, comorbidities, and concomitant medications will be assessed on cohort entry date or within 365 days prior to cohort entry date. Type of administration will be assessed on index date. The baseline characteristics of patients with menopausal symptoms will be presented in frequency (proportion) for categorical variables and mean (standard deviation, SD) or median (interquartile ranges, IQR) for continuous variables.
- All outcome variables will be summarized descriptively through tables or graphical forms, including means, medians, ranges, and standard deviations of continuous variables, as well as frequency distributions of categorical variables.
- We will evaluate annual and quarterly time-series trends in the prevalence of MHT between 2012 and 2020 from 4 dimensions: 1) treatment class of MHT: ET (estrogen therapy), EPT (estrogen-progestin therapy), and tibolone. 2) age group: all, 40-44, 45-49, 50-54, and 55-59. 3) menopausal symptoms: vasomotor symptoms, bone and joint symptoms, genitourinary symptoms, and psychosomatic symptoms. 4) type of administration: systemic HT (oral), systemic HT (transdermal), and local HT (transvaginal).
- For treatment change pattern analysis, the treatment will be categorized and the proportional flows of patients switching the treatment classes will be demonstrated by Sankey diagram.
- Kaplan-Meier survival curves will be generated to calculate the time to non-persistence events including switch and discontinuation. Discontinuation will be defined as no subsequent prescriptions within 2 months of last prescription date.
- Treatment persistence is calculated by the average length of treatment of the drugs prescribed at the index date. Persistence rate at 3-, 6-, 9-, and 12-month were also calculated.
- Treatment adherence will be evaluated using medication possession ratio (MPR) calculated as the total number of days of medication supply divided by the number of days in the follow-up period.

